5.0 Study Design*

5.1 *Describe and explain the study design (e.g. case-control, cross-sectional, ethnographic, experimental, interventional, longitudinal, observational).*

Response:

This study is a nonconcurrent multiple baseline design; participants will be randomized to a 6 week, 8 week, or 10 week staggered baseline periods followed by 4-8 weeks of Episodic Future Thinking (EFT).

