7	3/7/2020	Due to the ongoing concern in our area regarding COVID-19, we are updating sections 12 and 18 to allow for us to take precautions to ensure the safety of our participants and staff.	
8	4/7/2020	Updates for Covid-19	yes
9	7/22/2020	Updates for CR	no

FUNDING:

Indicate any funding for this proposal. This should match the Funding Sources page in Click IRB.

Response:

This study is funded by the grant “Delay Discounting as a target for self-regulation for prediabetics” funded by NIDDK RFA-RM-14-020, “Science of Behavior Change: Assay Development and Validation for Self-Regulation Targets (UH2)”.

GRANT APPLICABILITY:

Indicate whether this protocol is funded by a grant (e.g. NIH, foundation grant). For a grant with multiple aims, indicate which aims are covered by this research proposal.

NOTE: This question does not apply to studies funded by a sponsor contract.

 *Include a copy of the grant proposal with your submission.*

Response:

This study is funded by the grant “Delay Discounting as a target for self-regulation for prediabetics” funded by NIDDK RFA-RM-14-020, “Science of Behavior Change: Assay Development and Validation for Self-Regulation Targets (UH2)”. This study was submitted and approved in request to carry forward funds from the UH2, to UH3 phase of this grant; and covers all three specific aims outlined in the application for approval to keep the carryforward funds.

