We propose an RCT that will assess the effects of EFT on medication adherence, general PM, and DD among those with pre- or type 2 diabetes or related comorbidities who are currently taking at least one oral medication for diabetes or related comorbidities. We will recruit participants who are relatively non-adherent to an oral medication ($\leq 80\%$ of prescribed doses taken in the past month; to accommodate over-reporting) for prediabetes or type 2 diabetes or other conditions that commonly co-occur with these conditions (e.g., hypertension, hyperlipidemia). Medication adherence will be monitored using electronic pill bottle caps (MEMS caps, which record bottle openings with date and time stamps), pill counts, and pharmacy records. Medications for glucose control as well as control of hypertension and/or hyperlipidemia will be considered as targets for measurement. Participants self-rated as non-adherent ($\leq 80\%$ prescribed doses taken), and report difficulty remembering to take one’s medication as a primary reason for non-adherence, will undergo a 6 week, 8 week, or 10 week baseline period. After the staggered baseline periods, all participants will receive EFT intervention. In total, participants will be in baseline and treatment for a total of 15 weeks.

Randomized participants will complete bi-weekly in person sessions plus phone sessions for the weeks in which they do not come to the lab, in which they learn to engage in EFT for medication adherence. Initial EFT for medication adherence will focus on taking the targeted medication on a typical day (e.g., a weekday when the participant usually works), and in subsequent sessions EFT will be used to assist participants in adapting to unusual circumstances that may interrupt adherence or have been reported as contributing to non-adherence.

At an initial baseline session, post-intervention, and follow-up, participants will complete measures of working memory, lab-based PM, and DD. Dependent measures include change in targeted medication adherence (based on MEMS data), change in non-targeted medication adherence (for participants initially reporting non-adherence to multiple medications; based on self-report and pill count measures), DD, and PM. Moderators to be tested include working. The goal of the study will be to collect pilot data to test the feasibility and initial efficacy of the approach, as well as effect sizes for a subsequent R01.

4.2 Include complete citations or references.

Response:

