Participants will complete the major life events assessment and a variety of assessments pertaining to executive function/memory. Similar to the screening/baseline session, these measures will all be administered via Zoom. Some of these tasks may only be administered in certain assessment sessions (e.g., the initial and/or final).

The types of tasks participants may complete are:

- Prospective memory tasks
- A working memory task
- An impulsive choice task

Participants will also have their height/weight taken, and the research staff will obtain self-report and objective measures of medication adherence (e.g., information such as data from MEMS caps, pill counts, reasons for non-adherence, and reasons for opening medication bottles).

Intervention Sessions:

During the Covid-19 Quarantine All intervention sessions will be conducted via zoom.

During each intervention meeting, the research staff will obtain self-report and objective measures of medication adherence, and participants will either complete EFT or IC activities, dependent on group assignment. Pill counts and MEMS data may be obtained by a staff member that is not acting as the interventionist for EFT/IC activities, so as to reduce the total time the participant must be in the lab.

Participants assigned to EFT will be asked to generate episodic cues, similar to the tasks used in our previous studies on EFT's effect (Daniel et al., 2013); unlike in prior studies, however, cues will be specific to instances of taking one's medication and/or positive events resulting from successful medication adherence. The episodic component of the thinking task occurs while the participants are asked to describe the perceptual details of the medication-taking (e.g., taking medication at home on a typical day, or while out of town on vacation) or medication-outcome event (feeling better and more energetic after medication, etc.). Participants will be asked open-ended questions to prompt more detail (such as what they are seeing, hearing, smelling, feeling), and to identify what successful adherence may look like if the initial event description does not go as planned (e.g., if you normally take your medication when you make coffee, what would successfully taking your medication look like on a day when you run out of time to make it?). Participants may record their EFT events into audio cues, so that they can practice using EFT using different modalities at home.

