19.0 Data Management and Analysis*

19.1 Describe the data analysis plan, including any statistical procedures. This section applies to both quantitative and qualitative analysis.

Response:

Pill count and MEMS data displayed as a percentage of doses taken will be displayed graphically to enable visual analysis of changes in means and trends of dependent variables across the different phases of the study.

Borckardt, J., & Nash, M. (2014). Simulation modelling analysis for small sets of single-subject data collected over time. *Neuropsychological Rehabilitation*, 24(3-4), 492–506. <https://doi.org/10.1080/09602011.2014.895390>

19.2 If applicable, provide a power analysis.

NOTE: This may not apply to certain types of studies, including chart/records reviews, survey studies, or observational studies. This question is asked to elicit whether the investigator has an adequate sample size to achieve the study objectives and justify a conclusion.

Response:

A power analysis is not applicable to this multiple baseline design. We are collecting weekly data from participants and will have enough data points to ensure we will be able to achieve the study objectives. The results of this study will be analyzed graphically as well as assessing the degree of change from baseline to treatment across the three replications. For an example of a study that utilized a multiple baseline design, see:

19.3 Describe any procedures that will be used for quality control of collected data.

Response:

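### Section 19 compares adherence by study phase only, so in this nonconcurrent design a Covid-19-era calendar shift near a participant's EFT start could mimic or hide an EFT effect

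*Combined protocol and SAP*

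**What the plan says.** Section 5.1 sets out the design: "This study is a nonconcurrent multiple baseline design", with random assignment to "6 week, 8 week, or 10 week staggered baseline periods followed by 4-8 weeks" of EFT. Every participant eventually receives EFT.

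The revision log at the front has an entry dated 3/7/2020: "Due to the ongoing concern in our area regarding COVID-19, we are updating sections 12 and 18". A further Covid-19 update is dated 4/7/2020. Section 12.1 keeps in-person procedures beside Covid-19 alternatives for consent, assessment and MEMS handling, and says of EFT delivery: "During the Covid-19 Quarantine All intervention sessions will be conducted via zoom". Section 8.2 describes all sessions as remote because of Covid-19.

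The adherence analysis in 19.1 is a graphical display for "visual analysis of changes in means and trends of dependent variables across the different phases of the study". Section 19.2 adds "assessing the degree of change from baseline to treatment across the three replications". Neither mentions calendar date, the pandemic period or mode of conduct. Section 12.3 collects a major life events questionnaire and reasons for non-adherence, but section 19 gives neither a role.

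The dates needed are already being recorded. Section 4.1 describes "MEMS caps, which record bottle openings with date and time stamps".

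**The concern.** In a concurrent multiple baseline design, an outside event strikes all series on the same date, and the tiers still in baseline show whether adherence moved without treatment. In a nonconcurrent design the tiers need not share calendar weeks. Series lined up by study week give no untreated comparison on the date when a treated series changes, unless the data are also lined up by date.

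This outcome may be sensitive to such an event. The protocol names forgetting as a common reason for non-adherence (4.1), and its EFT examples tie doses to domestic routines (6.1, 12.1). That the pandemic altered participants' routines is a plausible assumption, not something the documents state.

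At stake are the Aim 1 conclusion and the effect sizes that this pilot is meant to supply for a later grant application (4.1). A shift could inflate or mask either.

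**Working it through.** **Inputs from the protocol.** The table in 13.2 gives baselines of b = 6, 8 or 10 weeks and EFT in weeks 7–14, 9–14 or 11–14, so t = 8, 6 or 4 weeks and b + t = 14. Its total hours confirm this: 0.5 + 2.5 + 2 × 2 + t × (0.2 + 0.58) gives 13.24, 11.68 and 10.12, as printed. Recruitment takes 4 months in 7.3 (4 × 52/12 = 17.3 weeks) and up to 6 months in 13.1 (26 weeks), so both are used. The goal is to randomise at least 10–12 (7.1). There is no stated power, SD or effect size to reproduce; 19.2 says "A power analysis is not applicable to this multiple baseline design".

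**Assumptions.** One lasting step shift of D points in adherence on one date, a true EFT effect of zero, and steady enrolment. D = 10 is illustrative; results scale with D and change sign with it.

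**Step 1: one participant.** Let the event fall e weeks into the series.

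False change = D × (share of EFT weeks after the event − share of baseline weeks after it).

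- If e ≤ b: D × [1 − (b − e)/b] = D × e/b.
- If e ≥ b: D × (14 − e)/t.

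With D = 10:

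| Baseline | Event 2 weeks before EFT start | At EFT start | 2 weeks after |
|---|---|---|---|
| 6 weeks | 4/6 → 6.7 | 10.0 | 6/8 → 7.5 |
| 8 weeks | 6/8 → 7.5 | 10.0 | 4/6 → 6.7 |
| 10 weeks | 8/10 → 8.0 | 10.0 | 2/4 → 5.0 |

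**Step 2: average over timing.** With e uniform on 0 to 14, the mean is (1/14) × (b/2 + t/2) = 14/28 = 0.50. Because b + t is always 14, this is the same in all three tiers. The stagger does not reduce it.

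**Step 3: group mean.** The largest fraction of series that can contain the date is 14/26 = 54% or 14/17.3 = 81%. Multiplying by 0.50 gives 27% or 40% of the shift, or 2.7 or 4.0 points for D = 10. These are upper bounds on the expected value. With 4-month recruitment, the bound is reached only if the event falls in a window of about 17.3 − 14 = 3.3 weeks. A simulation with whole-week entry dates agrees: 2.6 and 3.9 points at the worst event date, with 30% and 45% of participants showing a false change of 5 points or more. With 12 participants, chance bunching of entry dates takes the 97.5th percentile to 4.4 and 5.8 points.

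**Step 4: series most open to misreading.** An event within 2 weeks either side of EFT start affects up to 4/26 = 15% or 4/17.3 = 23% of participants, about 2 or 3 of 12.

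**Step 5: does a calendar term help?** Weekly data were simulated for 12 and 20 participants, with an assumed within-person SD of 15 points and shifts of ±10 or 0. They were analysed by regression on participant and phase, with and without a pre/post-event term.

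| | Phase only | With calendar term |
|---|---|---|
| Mean false EFT effect (points, absolute) | 2.4–4.0 | within 0.3 of zero |
| False positives at an illustrative two-sided 5% | 18–54% | 3–7% |

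With no shift, the term made the standard error about 7–22% larger. The plan specifies no test, so the error rates illustrate direction and order of size only.

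**The case against.** **Exposure is not shown.** The revision log dates protocol updates, not enrolments. If every series ran after the move to remote conduct, mode of conduct is constant and cannot confound, although other pandemic-period changes still could. This stands, and it makes the point conditional.

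**Plots would reveal much of it.** With staggered entry, one date falls at different study weeks in different people. A step in mid-baseline or mid-EFT would appear as a jump away from the phase line, and the plan does inspect trends. Reasons for non-adherence are also collected. This stands for steps far from EFT start. It fails for steps close to it, where a calendar jump and an EFT response look alike in study time. So a reader should not infer that comparing tiers can never expose a calendar effect.

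**Baseline length is randomised.** This gives partial protection. It moves EFT start by at most 4 weeks, and 12.1 passes unstable participants to the next baseline length, so the start is not purely random.

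**It is a pilot.** True, but it is meant to yield effect sizes, so bias would carry forward.

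A reader might also infer that the pandemic could explain a whole group result, or would favour EFT. Neither is supported. Under steady enrolment most of a single shift does not reach the group mean, and a fall in adherence would hide an EFT benefit.

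**Conclusion.** The gap is real, conditional and cheap to close, so it should be fixed. The design does not control for calendar events through the stagger alone, the protocol spans dated Covid-19 changes, and section 19 has no means of separating a calendar shift from an EFT response.

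The consequence is sharpest for individual series. With the event at EFT start the whole shift appears as EFT change, and within 2 weeks of it at least half does. For the group mean, the expected share is at most about 27–40%. This rests on a single lasting shift and steady enrolment. Bunched enrolment would raise the share, and a temporary shift would partly cancel in series containing both its start and its end. The 10-point shift is an assumption with no source in the documents. How many participants crossed the change, if any, is unknown.

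**What to change.** Add to 19.1:

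1. Using the MEMS date stamps, plot each series on a calendar axis as well as by study week, with the Covid-19 and remote-conduct dates marked.
2. Identify participants whose series cross those dates and, among them, those whose EFT start lies near them (for example within 2 weeks). If no series crosses, say so; the other steps then fall away.
3. Report the numerical baseline-to-EFT change with and without a pre/post calendar-period term, as a sensitivity analysis. Section 19 names no model, so state one, for example weekly adherence on participant and phase.
4. Report the change descriptively without the participants who cross the dates near EFT start, and qualify the Aim 1 conclusion if it depends on them.

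The Aim 1 conclusion should not be made to depend on agreement with the subset lying wholly on one side of the dates. At the largest straddling fractions that subset is 46% or 19% of 10–12 people, about 5 or 2, too few to confirm or refute anything.

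The cost is a few lines of text, a little programming and no new data. The adjusted estimate is less precise (standard error about 7–22% larger in the illustrative simulation). For participants whose EFT start coincides with the event, the calendar term is nearly collinear with phase, so the adjustment draws on the spread of entry dates among the others.

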6.0 Study Intervention/Investigational Agent

6.1 *Describe the study intervention and/or investigational agent (e.g., drug, device) that is being evaluated.*

Response:

The intervention being researched is called episodic future thinking (EFT), which consists of imagining specific instances of one's future. In this study, participants will engage in EFT focused on imagining taking one's medication, guided by a research staff member in their intervention sessions in addition to bi-weekly

check-in calls across a 4-8 week period. The research staff member will conduct the intervention session using a semi-structured interview format in which the staff member works to identify situations/circumstances in which the participant encounters challenges with taking their medication, and subsequently asking questions to prompt the participant to imagine what successful medication adherence would consist of (and “look” like). Sessions may also involve imagining positive events resulting from successful medication adherence and the details surrounding those events. For example: if the research staff member finds that a participant struggles to take their medication on weekends, the staff member will ask the participant to visualize what successfully doing so might entail (getting the medication bottle and putting it next to the waffle iron, which is frequently used on the weekends) and to imagine the sensory aspects of the experience of doing so (picking up the medication bottle, taking out the waffle iron, placing it on the counter—and noting any typically associated smells, items one sees, etc.).

6.2 Drug/Device Handling: If the research involves drugs or device, describe your plans to store, handle, and administer those drugs or devices so that they will be used only on subjects and be used only by authorized investigators.

- *If the control of the drugs or devices used in this protocol will be accomplished by following an established, approved organizational SOP (e.g., Research Pharmacy SOP for the Control of Investigational Drugs, etc.), please reference that SOP in this section.*

Response:

N/A

6.3 If the drug is investigational (has an IND) or the device has an IDE or a claim of abbreviated IDE (non-significant risk device), include the following information:

- *Identify the holder of the IND/IDE/Abbreviated IDE.*
- *Explain procedures followed to comply with sponsor requirements for FDA regulated research for the following:*

Response:

N/A

7.0 36 Local Number of Subjects

7.1 Indicate the total number of subjects that will be enrolled or records that will be reviewed locally.

Response:

Up to 20 subjects will be enrolled from Buffalo, and the neighboring cities. Subjects will be randomized after completion of the baseline period. The goal will be to randomize at least 10-12 participants.

7.2 If applicable, indicate how many subjects you expect to screen to reach your target sample (i.e. your screen failure rate).

Response:

We expect to initially screen approximately 60 subjects (online or by phone screen survey) and complete about 20 in person and baseline screenings.

7.3 Justify the feasibility of recruiting the proposed number of eligible subjects within the anticipated recruitment period. For example, how many potential subjects do you have access to? What percentage of those potential subjects do you need to recruit?

Response:

Given that we will be taking advantage of CTSI resources for recruiting based on individuals' diagnosed medical conditions, we anticipate that recruiting this relatively small number of participants for our final sample will be feasible within a 4-month period. The Buffalo Research Registry has 200-some potentially eligible individuals based on a diagnosis of Pre- or Type 2 Diabetes, and TriNetX an additional 15,110 with these diagnoses (with 5,150 of these prescribed an oral blood glucose-regulating medication).

8.0 Inclusion and Exclusion Criteria*

*8.1 Describe the criteria that define who will be **included** in your final study sample.*

NOTE: This may be done in bullet point fashion.

Response:

Adults over the age of 18 with prediabetes or Type 2 Diabetes currently prescribed at least one oral medication for blood glucose regulation, or for related comorbidities e.g., hypertension, hyperlipidemia, and are relatively non-adherent to taking them (< 80% of prescribed doses taken), but are motivated and/or have the intent to better comply with their medication regimen, will be studied.

During the Baseline Period, if participants are adherent to their medications (>80%), their participation in the study may be terminated.

Prediabetes and Type 2 Diabetes: Participants must report having have a diagnosis of prediabetes or Type 2 Diabetes within the last 2 years or meet criteria for prediabetes or Type 2 Diabetes. The American Diabetes Association guidelines (Group, 2003) defines prediabetes and Type 2 Diabetes as Fasting Plasma Glucose (FPG) 100mg/dl or greater, 2h glucose 140mg/dl or greater after Oral Glucose Tolerance Test (OGTT), or hemoglobin A1c (HbA1c) of approximately 5.4% or greater. We will also include individuals who have

increased risk for developing prediabetes and type 2 diabetes, which includes individuals who have a BMI of 30 or higher with one or more related comorbidities (e.g., hypertension, hyperlipidemia).

8.2 Describe the criteria that define who will be *excluded* from your final study sample.

NOTE: This may be done in bullet point fashion.

Response:

Pregnancy: Women who are pregnant or lactating will be excluded from participation.

Substance use, abuse, or dependence: Individuals that currently have problems with substance dependence, addiction, or problematic substance use that would limit participation (e.g., binge drinkers, alcoholics, daily stimulant/opiate users) will be excluded.

Conditions that affect adherence: Participants should not have a condition that would limit participation which include medical conditions that would affect individuals' ability to use the computer for prolonged period of time; leave the individual unable to ambulate; unmanaged psychiatric disorder (e.g., depression, anxiety, attention deficit hyperactivity disorder, schizophrenia), cognitive impairment that would impact memory (e.g., symptomatic concussion), or an intellectual impairment that would impact study adherence. Additionally, participants should be able to attend to all intervention sessions (Due to Covid-19 all sessions will be completed remotely/virtually) and have reliable access to technology required to complete the measures in this study. If a participant is not able to make most sessions (e.g. participant is out of town during most of the study for work or vacation travel), or does not have reliable access to technology, they may be excluded from the study.

Prior participation in similar studies: Individuals who have recently participated in a laboratory study using similar methods may also be excluded.

Use of medication adherence aids: individuals who currently use aids to assist with medication adherence (e.g., pill organizers, reminder apps) may be excluded.

8.3 Indicate specifically whether you will include any of the following special populations in your study using the checkboxes below.

NOTE: Members of special populations may not be targeted for enrollment in your study unless you indicate this in your inclusion criteria.

Response:

- Adults unable to consent
- Individuals who are not yet adults (infants, children, teenagers)

- Pregnant women
- Prisoners

8.4 *Indicate whether you will include non-English speaking individuals in your study. Provide justification if you will exclude non-English speaking individuals.*

*In order to meet one of the primary ethical principles of equitable selection of subjects, non-English speaking individuals may **not** be routinely excluded from research as a matter of convenience.*

In cases where the research is of therapeutic intent or is designed to investigate areas that would necessarily require certain populations who may not speak English, the researcher is required to make efforts to recruit and include non-English speaking individuals. However, there are studies in which it would be reasonable to limit subjects to those who speak English. Some examples include pilot studies, small unfunded studies with validated instruments not available in other languages, studies with numerous questionnaires, and some non-therapeutic studies which offer no direct benefit.

Response:

This study will not include non-English speaking participants. Since all the materials in this study will be in English, and the validated measurements are not provided in other languages, we will be excluding individuals who do not speak English.

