All participants complete a 6-week baseline in which they will use the MEMS bottles. At week 6, all participants will attend an in-person lab session to assess their adherence levels through looking at data from the MEMS bottles and pill counts.

Covid-19 Alternative Procedure: All participants will complete a 6-week baseline in which they will use the MEMS bottles. At week 6, data from the MEMS bottle will be obtained. In order to reduce participant and staff interaction due to COVID-19, this procedure will involve participants placing the cap from the MEMS bottle in a small bag placed in their mailbox. Research staff will conduct mobile data collection, and simply pick up the MEMS cap, and using sanitation

procedures, remotely download the data from the MEMS cap. The cap will then be returned to the participants mailbox.

Participants will then be randomly assigned to either the 6-week, 8- week or 10-week baseline. If a participant's medication adherence is not below 80%, they will be asked to come in at week 8 to reassess their adherence level (similarly, if their adherence is not below 80% at week 8, they will be asked to come back at week 10. If their adherence is not below 80% at this point, they will be dismissed from the study). If a participant is below 80% adherence within this 6-week period and their adherence is stable, meaning that there is no increasing trend in their adherence level, they will be randomly assigned to either a 6-week, 8- week or 10-week baseline. Participants who were assigned 6- week baseline, will now be eligible to start the intervention, those in the 8-week will complete two more weeks of baseline prior to the intervention, and those in the 10-week will complete four more weeks of baseline prior to the intervention *.

*Participants must be considered stable based on their pill counts to continue to the intervention period. For this study stability will be defined as no increasing trend (3 data points) in their adherence level. If a participant was assigned to a group but is not stable during that time period, they will be assigned to the next group (if disqualified for 6-week they will go to the 8-week and so on).

Assessment Sessions:

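### Section 8.1 permits termination for adherence above 80% after tier assignment, which can occur only in the 8- and 10-week tiers and, if those data are not displayed, could mask a rise before EFT

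*Combined protocol and SAP*

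**What the plan says.** Section 8.1 gives a permissive rule with no end point other than the end of baseline: "During the Baseline Period, if participants are adherent to their medications (>80%), their participation in the study may be terminated".

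Section 12.1 (Baseline Sessions) gives the operating sequence. First, "All participants complete a 6-week baseline in which they will use the MEMS bottles". Assignment then follows on a condition: "If a participant is below 80% adherence within this 6-week period and their adherence is stable". After assignment the tiers diverge:

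- 6-week tier: "Participants who were assigned 6- week baseline, will now be eligible to start the intervention"
- 8-week tier: "those in the 8-week will complete two more weeks of baseline prior to the intervention"
- 10-week tier: "those in the 10-week will complete four more weeks of baseline prior to the intervention"

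Section 12.1 also has its own handling of high or rising adherence. Someone not below 80% at week 6 is rechecked at weeks 8 and 10, and only then: "If their adherence is not below 80% at this point, they will be dismissed from the study". An assigned participant whose adherence is rising is moved on: "if disqualified for 6-week they will go to the 8-week and so on".

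Section 7.1 places randomization after baseline is complete, which does not fit the week-6 assignment in 12.1. Sections 19.1 and 19.2 rest on graphs, visual analysis of means and trends, and the change from baseline to treatment across the three tiers. Neither defines an analysis set or says how a participant terminated under 8.1 is shown. Section 22.3 allows, but does not require, data from people who withdraw to be kept and analyzed.

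**The concern.** Every tier receives EFT, so protection against drift over time or from electronic monitoring comes from the extended baselines. If adherence stays flat in weeks 7-10 among people who have not started EFT, a rise at the start of EFT is easier to credit to EFT. If adherence rises in those weeks, that counts against EFT.

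The 8.1 rule selects on that outcome. It permits removal of an assigned participant because adherence rose before EFT. It cannot act after assignment in the 6-week tier, which has no baseline left. It is also discretionary, and the plan does not say which window the 80% refers to. With a goal of 10-12 randomized participants, losing one or two series from the later tiers could change what a reader sees in the graphs.

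**Working it through.** The plan gives no power calculation or expected loss, so there is no figure of its own to reproduce.

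**1. Exposure after assignment.** Weeks exposed = tier length minus the common 6 weeks (12.1).

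- 6-week tier: 6 − 6 = 0
- 8-week tier: 8 − 6 = 2
- 10-week tier: 10 − 6 = 4

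Loss of assigned participants under 8.1 is therefore zero in the first tier by construction, and possible in the other two.

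**2. Chance of losing at least one person.** Section 7.1 aims for at least 10-12 randomized. Assuming equal allocation (the ratio is not stated), two thirds are exposed: 10 × 2/3 = 6.7 to 12 × 2/3 = 8, or about 7-8 people. P(at least one lost) = 1 − (1 − p)^n, where p is an assumed risk per person:

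| p | n = 7 | n = 8 |
|---|---|---|
| 10% | 0.52 | 0.57 |
| 20% | 0.79 | 0.83 |
| 30% | 0.92 | 0.94 |

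**3. Simulation with a common drift and no EFT effect.** All inputs are assumptions. True adherence has mean 65-70% and SD 10-12 points, with once-daily dosing. Doses taken in weeks 1-6 are binomial over 42 days, and only people below 80% are kept. A further 14 or 28 days follow with a drift of 0 or 10 points. The rule is always enforced. The visible rise is mean adherence in the added weeks minus mean adherence in weeks 1-6. It slightly exceeds the drift, because selecting people below 80% brings some regression to the mean.

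| Setting | Removed from 8- and 10-week tiers | Visible rise, 8-week | Visible rise, 10-week |
|---|---|---|---|
| +10 drift, nobody removed | 0 | about 11 | about 11 |
| +10 drift, rule on added weeks | 28-41% | 5.3-6.4 | 7.0-7.9 |
| +10 drift, rule on cumulative adherence | about 5-10% | falls by at most about 0.6 | falls by at most about 0.6 |
| No drift, rule on added weeks | 8-15% | – | – |

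Share of the rise lost when the rule is applied to the added weeks:

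- 8-week tier: (11 − 6.4)/11 = 42% to (11 − 5.3)/11 = 52%
- 10-week tier: (11 − 7.9)/11 = 28% to (11 − 7.0)/11 = 36%

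**4. The planned baseline-to-treatment change.** Same model with mean 67.5%, SD 11, +10 drift and the rule on the added weeks. Against the whole baseline, the null change goes from 8.3 to 9.1 points (8-week, +0.8) and from 6.6 to 7.4 (10-week, +0.8). Against the added weeks alone, the bias would be about 3-5 points.

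**5. A different null model.** Here 20-40% of people improve by 25 points at a random week from 1 to 14, without EFT. Assumed person mean is 65% (SD 10, capped below 80%) and weekly SD is 10 points. Removal applies if the mean of the added weeks exceeds 80%.

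- 10-16% of the later tiers are removed, including about 57% (8-week) and 48% (10-week) of those who improve between week 7 and the end of their baseline.
- The untreated rise shrinks from between +1.3 and +2.5 points to between −0.3 and +0.1 (8-week), and from between +1.7 and +3.3 to between +0.4 and +1.0 (10-week).
- Whole-baseline-to-treatment change falls slightly. With 40% improvers in the 8-week tier it goes from +4.9 to +4.2.

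**The case against.** The strongest reply is that 8.1 merely summarises the gate in 12.1. The operating text rechecks people before assignment and moves unstable assigned participants to a later tier. It contains no step that terminates an assigned person for passing 80%. Under 7.1 taken literally, no baseline would follow assignment at all. This reading is reasonable and may be what the sponsor meant. But 8.1 does not limit itself to the time before assignment, the 12.1 sequence does create baseline weeks after it, and the move-on rule offers no further tier to a 10-week participant. The three sections need reconciling whichever reading was intended.

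Two stronger readings are tempting and are not supported. A reader might infer that the plan hides evidence against EFT. No section says that people terminated under 8.1 are left off the graphs. The plan neither requires nor forbids showing them, so the loss of evidence is conditional. A reader might also infer that the rule makes EFT look effective on the planned comparison. Against the whole baseline the shift is under about 1 point, and its direction differs between the two models.

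The 28-41% is also an upper scenario. It needs a 10-point drift that begins only after week 6, although monitoring starts in week 1. It also needs the rule read on the added weeks alone, and a discretionary rule enforced every time.

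**Conclusion.** The point holds in conditional form. Sections 8.1 and 12.1, read together, permit discretionary, outcome-based removal of assigned participants in the 8- and 10-week tiers only. If their data are then omitted, some untreated improvement goes unseen. The extent cannot be known from the documents. It ranges from little bias under a cumulative reading to a quarter to a half of a common 10-point drift under an added-weeks reading. In the model with scattered improvers, most of a much smaller rise is lost. That the answer turns on an unstated window is itself a reason to fix the text. The exposure is mainly in the visual analysis, on which Section 19 leans, rather than in the mean change from whole baseline to treatment. It is a repairable weakness in a small pilot that deserves an amendment, and it does not invalidate the design.

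**What to change.** Reconcile 7.1, 8.1 and 12.1 on when assignment occurs and on what happens when adherence exceeds 80%. In 8.1, limit the termination rule to the period before assignment, for example:

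> Termination for adherence above 80% is an eligibility check made before tier assignment only. An assigned participant is not terminated because adherence rises during the remaining baseline.

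In 8.1 or 12.1, state the data source and the window over which the 80% is calculated. In 19.1, add that baseline data of every assigned participant, including anyone terminated for adherence above 80%, are kept, displayed and reported by assigned tier, with the number and reason for each termination.

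The cost is a short amendment. Displaying the data costs nothing. Keeping assigned participants means that some enter EFT with little room to improve. If drift is large this may be more than a few, since those kept are the same people the rule would have removed (up to 28-41% of the later tiers in the upper scenario). Those near-ceiling series should be identifiable in the graphs.
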